#### 4.3.3 Multiple Comparisons/Multiplicity

Treatment group comparison for the primary efficacy endpoint will be conducted at  $\alpha = 0.05$  (2-sided). No multiplicity adjustments will be performed for other efficacy analyses including sensitivity analysis based on non-responder imputation and supplemental analysis based on PPS.

#### 4.3.4 Examination of Subgroups

Various subgroup analyses are planned and pre-specified as described in each analysis section in this SAP. No hypothesis testing will be performed in the subgroup analyses.

The subgroups include: BMI category ( $<25$ ;  $\geq 25 \text{ kg/m}^2$ ), SUA level category ( $<9$ ;  $9 \text{ to } <10$ ;  $10 \text{ to } <11$ ;  $\geq 11 \text{ mg/dL}$ ), and classification of hyperuricemia (overproduction type, underexcretion type, combined type, other type).

BMI and SUA category are those assessed at the baseline. Classification of hyperuricemia group is defined as entered on the study CRF.

#### 4.3.5 Handling of Missing Data, Dropouts, and Outliers

Specific methods for handling missing values in analyzing the primary and secondary endpoints are detailed in each section. In general, missing values due to subject discontinuation, missed or unusable assessments will not be imputed unless otherwise specified.

#### 4.3.6 Other Considerations

Not applicable.

### 4.4 Efficacy Analyses

The FAS will be used as the primary population for all efficacy analyses. The unit of SUA will be based on mg/dL for all efficacy analyses.

#### 4.4.1 Primary Efficacy Analyses

The analysis for the difference in the proportion of subjects with  $\leq 6.0 \text{ mg/dL}$  in SUA level (i.e., responder rate) at Week 24 (LOCF) (see section 7) between dotinurad 4 mg and febuxostat 40 mg will be conducted based on a Cochran–Mantel–Haenszel (CMH) test stratified by baseline SUA level and baseline BMI. The difference in responder rate between dotinurad 4 mg and febuxostat 40 mg and the stratified 95% confidence interval based on Mantel–Haenszel method adjusting for the baseline SUA level and baseline BMI will be estimated. Also, the number (percentage) of responder and the asymptotic 95% confidence interval will be presented by treatment group. The same primary efficacy analysis mentioned above will be repeated supplementally based on the PP Analysis Set.

For the primary efficacy endpoint, non-responder imputation method on FAS will also be implemented as a sensitivity analysis, which will handle the missing data of SUA at Week 24 as non-responder (see section 7).

The following subgroup will be investigated for the responder rate at Week 24 (LOCF):

- SUA level category ( $<9$ ;  $9 \text{ to } <10$ ;  $10 \text{ to } <11$ ;  $\geq 11 \text{ mg/dL}$ )

- BMI category ( $<25$ ;  $\geq 25$  kg/m $^2$ )
- Classification of hyperuricemia (overproduction type, underexcretion type, combined type, other type)

For the subgroup analyses, the number (percentage) of responder and the 95% confidence interval will be presented by treatment group. Furthermore, the difference in responder rate and unstratified 95% confidence interval will also be presented.

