#### **Treatment I and II Phases**

Blood samplings for the assessment of SUA level will be conducted at approximately the same time at Weeks 4, 8, 12, 16, 20, and 24, or Early Termination Visit. The sampling date and time at each blood sampling point will be recorded in the CRF.

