**Table 3 Schedule of Procedures/Assessments in Study FYU-981-J086-301**

Phase	Screening	Treatment I		Treatment II					ET a	Unscheduled o
Visit	1	2	3	4	5	6	7	8		
Week	-4	0 b	4 c	8	12 d	16	20	24 e		
Day	-28	0	28	56	84	112	140	168		
Possible Study Day(s) Given Window	-28 to -4	0	23 to 33	51 to 61	77 to 91	105 to 119	133 to 147	161 to 175		
Procedures/Assessments										
Clinical laboratory tests j	X		X	X	X	X	X	X	X	
Viral screening k	X									
Serum uric acid level l	X		X	X	X	X	X	X	X	
Serum β-hCG (or hCG) test m	X							X	X	
Classification of hyperuricemia p	X									
eGFR	X									
12-lead ECG n	X				X			X	X	X
Abdominal ultrasound /abdominal radiography	X							X	X	

X: required done.

$\beta$ -hCG = beta-human chorionic gonadotropin (or hCG = human chorionic gonadotropin); CRF = case report form; ECG = electrocardiogram; eGFR = estimated glomerular filtration rate; ET = early termination; HBsAg = hepatitis B surface antigen; HCV = hepatitis C virus; HIV = human immunodeficiency virus; SUA = serum uric acid.

- a: These assessments will be conducted for subjects who discontinued the study early for any reason after Visit 2.
- b: Subjects who have developed gouty arthritis attack after the randomization day and before taking the first study drug are not to receive the study drug, and the subjects are to be discontinued from the study.
- c: Subjects who have developed gouty arthritis that has not disappeared by Week 4, are to continue to take the current investigational product without increasing dose for up to 1 week after the specified visit date (ie, up to Day 35) until the event disappears, and following the resolution of event, the study drug with increasing dose is to be dispensed at an Unscheduled Visit (ie, before or on Day 35) to the recovered subject. If the gouty arthritis does not disappear by 1 week or shorter after the specified visit day (ie, within Day 35), the subject is to be discontinued from the study treatment.

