## 4.2 Study Subjects

### 4.2.1 Definitions of Analysis Sets

Safety Analysis Set is the group of subjects who received at least 1 dose of study drug and had at least 1 postdose safety assessment.

Full Analysis Set (FAS) is the group of randomized subjects who received at least 1 dose of study drug and had at least 1 postdose primary efficacy measurement (ie, SUA level).

Per Protocol (PP) Analysis Set is the subset of subjects in the Full Analysis Set, who had no major protocol deviation(s) that may include but not limited to: lower study drug compliance less than 80%, administration of prohibited drug. The criteria for exclusion in this analysis set will be made and documented on a case-by-case basis from the viewpoint of reasonable clinical judgment prior to treatment unblinding.

The number (percentage) of randomized subjects in each analysis set will be summarized by treatment groups. The summaries for FAS will be based on subjects “as randomized”. The summary for Safety Analysis Set will be based on subjects “as treated”. Subject data listing for adoption of each analysis set will be listed.

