### 4.2.2 Subject Disposition

The number of subjects screened, the number and percentage of screen failures, and their primary reason for screen failure will be summarized. Screen failure data will be listed.

The number and percentage of randomized subjects will be summarized by sites for each treatment group.

The number of subjects who received study drug and completed the study will be presented. Subjects who prematurely terminated their participation in the study will be summarized by

their primary reason for study termination. Other reasons for study drug and study termination will also be summarized. These tabulations will be produced for all randomized subjects by treatment group. Subject-disposition data will be listed.

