#### Missing data handling

- Non-responder imputation for responder analysis of SUA (as binary variable)  
Missing values will be considered as non-responders. This handling will be applied to the sensitivity analysis of the primary efficacy analysis.
- Longitudinal data analysis of SUA using MMRM (as continuous variable)  
SUA will be analyzed using MMRM based on the assumption of missing at random (i.e., MAR). This analysis assumes subjects with missing values behave the same as the observed data within that treatment group, i.e., the missingness is independent of unobserved data after accounting for the observed data in the model.
- AE severity and AE relationship to study drug  
For the purpose of summarizing maximum severity, if the severity of an AE is missing for a subject, then, if this subject has another AE with the same preferred term that has “severe” severity, the maximum severity of the AE will be noted as “severe”; otherwise the maximum severity will be noted as missing. Similarly, for the purpose of summarizing treatment-related TEAE, if the relationship of an AE to study drug is missing, the AE will be noted to be related.
- Determination of TEMAVs for laboratory values  
For determining TEMAVs of laboratory values, a missing baseline laboratory value will be assumed to be of grade 0.

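### The non-responder imputation analysis is confined to the FAS, so dosed subjects with no post-dose SUA are missing from both the primary analysis and its only missing-data check

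*SAP*

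**What the plan says.** The primary endpoint is the proportion of subjects with SUA at or below 6.0 mg/dL at Week 24 (LOCF), compared by a CMH test stratified by baseline SUA and BMI. On the population, SAP 4.4 states: "The FAS will be used as the primary population for all efficacy analyses". SAP 4.2.1 defines the FAS as the "group of randomized subjects who received at least 1 dose of study drug and had at least 1 postdose primary efficacy measurement".

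For missing data on the primary endpoint, SAP 4.4.1 says the "non-responder imputation method on FAS will also be implemented as a sensitivity analysis", treating a missing Week 24 SUA as non-response. SAP Section 7, under missing data handling, repeats the rule, "Missing values will be considered as non-responders", and names no wider population. SAP 4.3.3 keeps this analysis outside the formal error control: "No multiplicity adjustments will be performed for other efficacy analyses including sensitivity analysis based on non-responder imputation".

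On sampling, protocol 9.5.1.2.1 says post-dose SUA sampling "will be conducted at approximately the same time at Weeks 4, 8, 12, 16, 20, and 24", or at an early-termination visit. Footnote a to protocol Table 3 says of that visit: "These assessments will be conducted for subjects who discontinued the study early for any reason after Visit 2". Protocol 9.5.5 asks for these procedures only where they are possible, and follows subjects who stop attending by mail, telephone or similar means.

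**The concern.** Non-responder imputation (NRI) is there to show what happens to the result if subjects without a Week 24 value are treated as failures. Subjects with no post-dose value at all have the most missing data, yet they are removed before the rule is applied. Having a post-dose SUA is determined after randomisation. If early loss without a sample differs between arms, neither the primary analysis nor its stress test reflects it.

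What is at stake is how robust the result appears. The primary p-value does not change, since alpha is assigned only to the primary comparison.

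**Working it through.** **1. Who is left out.** Each planned analysis that might cover a dosed subject with no post-dose SUA:

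| Planned analysis | Is the subject included? |
|---|---|
| Primary CMH, Week 24 (LOCF) | No: run on the FAS, and there is no value to carry forward |
| NRI sensitivity analysis | No: run on the FAS |
| Per-protocol repeat | No: the PP set is a subset of the FAS (SAP 4.2.1) |
| MMRM | No: it models continuous percent reduction from Week 4 onward (SAP 4.4.2), not response |

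**2. How large the group can be.** Several routes shrink it: the early-termination SUA, unscheduled SUA at the investigator's discretion (protocol Table 3, footnote o), and a Week 4 analysis window that opens on Day 2 (SAP Table 2). What remains is mainly loss before Week 4 with no sample of any kind. The documents give no rate for this.

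**3. The plan's own figure.** SAP Section 3 gives 225 per arm, 45% versus 60%, two-sided 0.05, power about 90%. With the pooled null variance and p̄ = 0.525:

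Φ[(0.15 × √225 − 1.96 × √(2 × 0.525 × 0.475)) / √(0.45 × 0.55 + 0.60 × 0.40)] = Φ[(2.250 − 1.384) / 0.698] = Φ(1.24) = 89.3%.

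This reproduces the stated power, so the same rates are used below.

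**4. Effect on the estimate.** Assume 225 dosed per arm, of whom k have no post-dose SUA, FAS rates of 60% and 45%, and no other missing Week 24 values. NRI on the FAS then gives 60.0% − 45.0% = +15.0 points whatever k is. NRI on all dosed subjects gives, per arm, FAS rate × (225 − k)/225. Pairs are dotinurad/febuxostat:

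- 5/5: 0.60 × 220/225 = 58.7%; 0.45 × 220/225 = 44.0%; difference +14.7
- 11/5: 0.60 × 214/225 = 57.1%; 44.0%; difference +13.1
- 5/11: 58.7%; 0.45 × 214/225 = 42.8%; difference +15.9

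**5. Chance that the two versions disagree.** Let X₁ ~ Bin(225 − k₁, 0.60) and X₂ ~ Bin(225 − k₂, 0.45), with the excluded subjects as fixed failures. The FAS version is the pooled z-test on X₁/(225 − k₁) versus X₂/(225 − k₂); the all-dosed version uses denominators of 225. Each is two-sided at 5%, counted as significant when dotinurad is better. Summing exactly over all outcomes:

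| Excluded (dot/feb) | P(sig), FAS | P(sig), all dosed | Only FAS sig | Only all-dosed sig |
|---|---|---|---|---|
| 5/5 | 0.886 | 0.886 | 0.0% | 0.0% |
| 2/0 | 0.894 | 0.875 | 1.9% | 0 |
| 5/1 | 0.889 | 0.848 | 4.1% | 0 |
| 11/5 | 0.878 | 0.807 | 7.2% | 0 |
| 0/2 | 0.896 | 0.912 | 0 | 1.6% |
| 1/5 | 0.892 | 0.924 | 0 | 3.1% |
| 5/11 | 0.882 | 0.930 | 0 | 4.8% |

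**6. Range with other missing data.** Suppose Week 24 SUA is also missing for 12% (dotinurad) and 6% (febuxostat) of the FAS, again an assumption. The NRI rates on the FAS become 0.88 × 60% = 52.8% and 0.94 × 45% = 42.3%, a difference of +10.5. The all-dosed differences are +10.3 (5/5), +8.9 (11/5) and +11.4 (5/11). Only the FAS version is significant in 3.7% (2/0), 7.5% (5/1) and 11.5% (11/5) of trials. In the mirror cases only the all-dosed version is significant in 3.6% (0/2), 7.1% (1/5) and 10.4% (5/11). Here the planned NRI already captures most of the missing-data effect: it takes the difference from 15.0 to 10.5, and the excluded subjects move it by at most about 1.7 points more in these cases.

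The planned test is stratified, so actual values would differ slightly from these unstratified ones.

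**The case against.** The population is a disclosed choice. The FAS definition is the same in the protocol and the SAP, the SAP names the FAS explicitly for this analysis, and the analysis is not confirmatory. That is right: nothing here is contradictory, and the point is about coverage.

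Much can also be recovered from planned output. SAP 4.2.1 tabulates each analysis set by arm, and SAP 4.2.2 reports "The number of subjects who received study drug", so the excluded count is dosed minus FAS. An unstratified all-dosed rate is then FAS responders divided by dosed subjects. This stands too; what the plan lacks is the stratified, prespecified result. The SAP's allowance for additional analyses does not supply one.

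The larger disagreement figures need 11 of 225 (4.9%) in one arm with no sample of any kind, plus a more than twofold imbalance. No document supports that. These cases are upper illustrations, not forecasts.

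Two objections concern the remedy. Replacing the FAS version would change the population and the imputation rule together, so a departure from the primary result could not be assigned to either. Requiring a dose is also a post-randomisation condition, so subjects randomised but never dosed stay out. Both are fair refinements, and neither makes the change unsound.

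**Conclusion.** The concern holds as a reading of the SAP: a dosed subject with no post-dose SUA is outside the primary analysis, its only missing-data sensitivity analysis, and every other planned responder analysis. The consequence is minor. With balanced loss of 5 per arm the estimate moves by 0.3 points and the two versions never disagree. With the assumed imbalances, and 60% versus 45% in the FAS, the estimate moves by up to about 2 points and significance differs in roughly 2% to 7% of trials, in either direction. The upper figure reaches 11.5% in the lower-rate scenario. All excluded counts, and the 12% and 6% missing rates, are assumptions. The textual reading is secure; the size in this trial cannot be known from the documents.

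**What to change.** In SAP 4.4.1 and Section 7, define the NRI sensitivity analysis on all randomised subjects who took at least one dose, without requiring a post-dose SUA. Count every subject without a usable Week 24 SUA as a non-responder, and use the same CMH strata, since baseline SUA and BMI are known from screening. The sentence should also cover a subject whose only sample was hemolysed or lipemic. Section 7 bars such values from efficacy analysis but does not say whether that subject meets the FAS criterion.

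Keep LOCF on the FAS as the primary analysis. Showing the FAS version of NRI beside the new one would separate the effect of the population from that of the imputation rule.

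The cost is one sentence and one extra program run. It needs no new data and no change to the endpoint, the FAS or the primary test. The downside is slightly lower responder rates in the sensitivity analysis. If no such subjects occur, the two versions coincide.

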#### 9.4.7.1 Prohibited Concomitant Drug and Therapy

Following drugs are prohibited within 14 days prior to screening and during the study.

1. Drugs to treat gout and hyperuricemia
  - 1) Uricosuric drugs (probencid, bucolome, benzbromarone)
  - 2) Uric acid production-inhibitory drugs (allopurinol, febuxostat [except the investigational product])
  - 3) Prophylaxis for gout flare (that includes colchicine, NSAIDs, corticosteroids, et al; and does not include topical application)
2. Drugs that affect the SUA level
  - 1) Salicylic acid-based antipyretics and analgesics (except aspirin taken to control thromboembolism formation, and salicylamide)
3. Drugs that potentially interact with the test drug
  - 1) Mercaptopurine hydrate
  - 2) Azathioprine
  - 3) Vidarabine
  - 4) Hexamine

If a medication (including in Chinese traditional medicine) is not on the list of prohibited medications but in the opinion of the investigator, which also can be used to treat gout/hyperuricemia, it must not be used throughout the study. If a medication is not specified as prohibited but is in the same class as a medication that is listed in the protocol, and if the investigator is uncertain, the Medical Monitor must be consulted. If a subject starts any prohibited medication or therapy during the study, he/she must discontinue from the study, with the exception that certain prohibited medications must be used to particular condition if this is agreed with the Medical Monitor.

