#### 9.5.5 Completion/Discontinuation of Subjects

A subject may elect to discontinue the study at any time for any reason. Wherever possible, all subjects who discontinue the study are to complete the study's early discontinuation procedures indicated in the Schedule of Procedures/Assessments ([Table 3](#)).

Subjects who meet any of the following criteria will be discontinued from the study:

1. Subjects who withdrew consent
2. Subject choice (eg, change in residence)
3. Subjects who had AEs leading to discontinuation from the study
4. Subjects who were considered impossible to continue the study due to progression of gout or inadequate therapeutic effect of the study drug by the investigator
5. Subjects who take prohibited concomitant drugs during the study, and the use is considered to interfere with the efficacy assessments and affect the subject's safety by the investigator, following consultation with the sponsor
6. Subjects who change the dosage and/or administration, or initiate any restricted concomitant drugs during the study, and the change or initiation is considered to interfere with the efficacy assessments and affect the subject's safety by the investigator, following consultation with the sponsor
7. Subjects who begin to routinely receive NSAIDs or corticosteroids (not including topical application) for a disease other than gouty arthritis
8. Subjects who developed gouty arthritis attack after the randomization day and before taking the first study drug
9. Subjects who developed gouty arthritis at Week 4 or 12, and the gouty arthritis did not disappear within 1 week after the specified visit date of Week 4 or 12
10. Subjects who developed nephrolithiasis (including clinical urinary calculi) after the first study treatment (excluding at the final visit)

11. Subjects who developed acute kidney injury (AKI) after the first study treatment (excluding at the final visit)

AKI is defined as any of the following (Kidney Disease: Improving Global Outcomes [KDIGO] 2012):

- Increase in serum creatinine (SCr) by  $\geq 0.3$  mg/dL ( $\geq 26.5$   $\mu$ mol/L) within 48 hours; or
- Increase in SCr to  $\geq 1.5$  times baseline, which is known or presumed to have occurred within the prior 7 days; or
- Urine volume  $<0.5$  mL/kg/h for 6 hours

12. Subjects with SUA level of  $\leq 2.0$  mg/dL for 2 consecutive visits (excluding at the final visit)

13. Subjects with AST or ALT level of  $5 \times$  ULN (excluding at the final visit)

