### 3 DETERMINATION OF SAMPLE SIZE

For the responder rate, assuming a rate of 45% for febuxostat 40 mg and 60% for dotinurad 4 mg, a sample size of 225 subjects in each group provides approximately 90% power to detect a between-group difference in the proportion of responders based on a two-group Chi-square test with a 0.05 two-sided significance level. The primary efficacy analysis is based on the FAS. Hence, 450 is the target number of subjects as the FAS.

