**Table 2 Windowing Rules**

Week	Target Visit Date (Study day)	Visit Window (Study day)
Week 24 (LOCF) c d	—	—
End of Treatment e	—	—

- a The last non-missing values including unscheduled assessments on or prior to the date of first dose.
- b The last non-missing values including unscheduled assessments up to Day 98 (inclusive) will be carried forward as the data for the efficacy analysis, which is known as Week 12 (LOCF).
- c The last non-missing values including unscheduled assessments up to Day 182 (inclusive) will be carried forward as the data for the efficacy analysis, which is known as Week 24 (LOCF).
- d For subjects who discontinued the study, the last non-missing values up to 14 days after the date of last dose will be carried forward as the data for the efficacy analysis.
- e The last non-missing values including unscheduled assessments during the study will be used for the safety analysis only.

In case of multiple assessments within the same visit window, the assessment closest to the target visit day will be used in data analyses; in the event of two assessments being equally close to the scheduled visit day, the latest assessment in time will be used. In the event of two assessments being equally close to the scheduled visit day, the data will be considered in an individual case.

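### Week 24 (LOCF) can credit the assigned drug with an SUA value reached on another urate-lowering drug; NRI shares the gap only for values observed in the Week 24 window

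*SAP*

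**What the plan says.** **Primary value.** SAP Section 7, Table 2, footnote c defines Week 24 (LOCF) as the last non-missing SUA up to and including Day 182, unscheduled samples included. Footnote d adds a limit: "For subjects who discontinued the study, the last non-missing values up to 14 days after the date of last dose" are carried forward. Neither footnote refers to other urate-lowering drugs.

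**Sensitivity analysis.** SAP 4.4.1 adds non-responder imputation (NRI), "which will handle the missing data of SUA at Week 24 as non-responder". The Week 24 window in Table 2 is Day 155 to Day 182.

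**Values set aside.** The only observed SUA results that SAP Section 7 removes from the efficacy analysis are those from hemolyzed or lipemic samples.

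**Prohibited drugs.** Protocol 9.4.7.1 bans other uricosurics, allopurinol and non-study febuxostat. Starting a prohibited drug requires discontinuation, "with the exception that certain prohibited medications must be used to particular condition if this is agreed with the Medical Monitor". Criterion 5 of Protocol 9.5.5 is worded more narrowly: it applies when "the use is considered to interfere with the efficacy assessments and affect the subject's safety by the investigator", after consultation with the sponsor.

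**Per-protocol set.** SAP 4.2.1 names "lower study drug compliance less than 80%, administration of prohibited drug" among the deviations that may exclude a subject. Exclusions are decided case by case before unblinding, and the PP analysis is supplementary.

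**The concern.** The primary question is how dotinurad 4 mg compares with febuxostat 40 mg on reaching the SUA target. If a third drug brings a subject to target, the assigned arm gets the credit. Two routes are open on the text.

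1. **Retained on a prohibited drug.** Through the Medical Monitor exception, or because criterion 5 is judged not to be met, a subject could reach Week 24 while taking one.
2. **Stopped, switched, then sampled.** Criterion 4 of Protocol 9.5.5 withdraws subjects for inadequate effect, and these are plausible candidates for other therapy. The early termination visit includes SUA. If the new drug is started before that sample, and the sample falls within 14 days of last dose, the value enters the primary analysis.

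Each such subject moves one arm's responder rate by 1/225 = 0.44 points. The PP analysis does not repair this: an excluded subject leaves the denominator, whereas a treatment failure should stay in it.

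**Working it through.** **Step 1: which analysis counts which value.** The rules, applied to an SUA of 6.0 mg/dL or less measured after the switch:

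| Subject | Week 24 (LOCF) | NRI |
|---|---|---|
| Retained on the other drug, sampled Day 155–182 | Responder | Responder |
| Discontinued, sampled Day 155–182, within 14 days of last dose | Responder | Responder |
| Discontinued, sampled before Day 155, within 14 days of last dose | Responder | Non-responder (no Week 24 value) |
| Discontinued, sampled more than 14 days after last dose | Value not used | Non-responder if before Day 155; if Day 155–182, no stated limit applies |

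The 14-day limit is attached only to the LOCF rows of Table 2. The primary analysis is thus exposed on both routes, and NRI only when the value lies in the Week 24 window.

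**Step 2: reproduce the plan's power.** The inputs are in SAP Section 3. The responder rates are given as "assuming a rate of 45% for febuxostat 40 mg and 60% for dotinurad 4 mg". On size and power, the section states that "a sample size of 225 subjects in each group provides approximately 90% power". The test is run at the "0.05 two-sided significance level".

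Power = Φ[(d − 1.96·SE0)/SE1], where d = pD − pF, p̄ = (pF + pD)/2, SE0 = √[2p̄(1 − p̄)/225] and SE1 = √[pF(1 − pF)/225 + pD(1 − pD)/225].

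With 0.45 and 0.60: SE0 = 0.04708, SE1 = 0.04655, and (0.15 − 0.09228)/0.04655 = 1.240. Power is 89.3%, so the stated figure of about 90% stands.

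**Step 3: add affected subjects.** Let kF and kD be the numbers wrongly counted as responders, so pF = 0.45 + kF/225 and pD = 0.60 + kD/225. The documents give neither number, so every row after the first is an assumption.

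| kF | kD | pF | pD | Difference (points) | Power |
|---|---|---|---|---|---|
| 0 | 0 | 45.0% | 60.0% | 15.0 | 89.3% |
| 2 | 0 | 45.9% | 60.0% | 14.1 | 85.3% |
| 3 | 0 | 46.3% | 60.0% | 13.7 | 83.0% |
| 5 | 0 | 47.2% | 60.0% | 12.8 | 77.8% |
| 5 | 3.6 | 47.2% | 61.6% | 14.4 | 86.8% |
| 2 | 2 | 45.9% | 60.9% | 15.0 | 89.3% |
| 5 | 5 | 47.2% | 62.2% | 15.0 | 89.4% |

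The 3.6 comes from sharing affected subjects in proportion to planned non-responders, 55% to 40%: 5 × 40/55 = 3.6.

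**Step 4: the other direction.** Suppose both true rates are 45% and 5 dotinurad subjects only are affected. Then pD = 0.4722, d = 0.0222, SE0 = 0.04700 and SE1 = 0.04699. (0.0222 − 1.96 × 0.04700)/0.04699 = −1.49, and Φ(−1.49) is about 6.8%. The chance of a significant result favouring dotinurad rises from 2.5% to about 6.8%.

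**The case against.** The case for leaving the plan alone has four parts.

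- **Few cases.** The protocol bans these drugs and discontinues subjects who start one. The exception covers certain drugs for a particular condition, the prohibited list includes drugs that are not urate-lowering, and nothing says the exception permits a replacement urate-lowering drug. No SUA sample is scheduled after the early termination visit. This stands: numbers should be small if the prohibition is followed.
- **NRI already answers it.** A reader might infer that the primary and NRI analyses are equally affected. The documents do not support that: a subject who switches, leaves and is sampled before Day 155 has no Week 24 value and is a non-responder under NRI. What remains is subjects retained to Week 24 or leaving late.
- **The effect is one-sided only by assumption.** A reader might infer that the gap must cost power because the weaker arm gains more responders. The figure of 77.8% puts every affected subject on febuxostat. Subjects not at target exist in both arms, and equal counts leave power unchanged. The direction is not known in advance.
- **Other safeguards exist, and using observed SUA regardless of other drugs is a recognised strategy.** Prohibited-drug use is reviewed as a deviation before unblinding and concomitant medications are tabulated by arm, so affected subjects could be traced. But none of this changes how they are classified, and the SAP does not state that it has chosen that strategy.

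**Conclusion.** The gap is real for the primary analysis and partial for NRI. As written, the Week 24 (LOCF) rule credits the assigned drug with an SUA value reached on another urate-lowering drug. The misstatement can go either way and is probably small. The scenarios calculated run from 77.8% power (5 febuxostat subjects only), through 86.8% (5 and about 3.6), to no loss (equal counts); in the opposite direction, a 2.5% chance of a false result favouring dotinurad becomes about 6.8%. All rest on assumed counts and an assumed split between arms, and on 45% and 60% being the rates without such values. They show sensitivity to a handful of subjects and are not a forecast. The point deserves correction because the SAP's own sensitivity analysis does not fully cover it and the remedy is cheap.

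**What to change.** In SAP 4.4.1 and Section 7, before unblinding:

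1. State that a subject whose SUA was measured on or after first intake of a prohibited urate-lowering drug is a non-responder at Week 24. Apply this at minimum in the NRI analysis and preferably also in the primary responder analysis.
2. State that this includes a subject with no earlier post-dose SUA, who stays in the FAS.
3. Set such values to missing in the MMRM.
4. Fix the list of qualifying drugs in blinded review.
5. Report the number of affected subjects by arm.

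Non-response is preferable to carrying forward the last value before the switch. For dotinurad, that value may come from the 1 mg or 2 mg period, whereas the primary question concerns 4 mg, and it leaves a subject with no earlier post-dose value undefined.

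Separately, Protocol 9.4.7.1 and criterion 5 of Protocol 9.5.5 differ on when prohibited-drug use leads to discontinuation and must be reconciled. No view is taken here on which clinical rule is right.

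The cost is a blinded flag on medication data already recorded and coded, and a few SAP sentences. The downside is that a few observed values are set aside.
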